# 334 4.5 NIDDK Project Scientists

The NIDDK Project Scientists' primary responsibility is to provide scientific support in all
aspects of the ICCTG Study, including protocol development, quality assurance and
quality control, interim data monitoring, final data analysis and interpretation, preparation
of publications, and group performance. All clinical sites and the DCC are subject to
official NIH site visits.Participant Criteria

## 340 5 Participant Criteria

- 341 5.1 Study population
- The study population for this RCT protocol will be drawn from patients with a diagnosis
  of IC, confirmed sometime in the past with the results from a cystoscopy/hydrodistention.
  Any IC patient presenting with symptoms of urinary frequency in conjunction with
  urinary pain/discomfort persisting for at least 24 weeks will be considered a candidate for
  enrollment into the study.
- 347 5.2 Number of participants and study duration
- This RCT will require the accrual of 136 participants, randomizing 34 participants to each
  of the 4 treatment arms. Assuming an annual accrual rate of approximately 35 participants
  for each of the 5 primary Clinical Centers (includes Satellite Centers and Affiliate Center),
  the total accrual for this protocol is expected to require 10 months. Allowing for a
  minimum of 24 weeks follow-up on all participants, this yields a total study length of
  approximately 16 months.
- 354 5.3 Inclusion criteria
- 355 Participants are required to fulfill the following criteria:
- **356** 1. Participant must be at least 18 years of age.
- **357** 2. Participant must sign and date the informed consent.
- 358 3. Participant (male or female) must agree to use an effective method of birth control.
- 359
  360
  361
  4. Participant must report a urinary frequency of at least 11 times per 24-hour day, on average over the previous four weeks. This frequency criterion must be met at each of the two baseline-screening visits as reported by the participant.
- 362 5. Participant must report a pain/discomfort score of 4 or greater on a 0 9 Likert
  363 scale. This pain/discomfort criterion must be met at each of the two baseline364 screening visits.
- 365
  366
  367
  6. These reported urinary symptoms of frequency and pain/discomfort must have been present for at least the previous 24 weeks prior to the first baseline screening visit (B1).

368	5.4	Exclusion criteria
369 370	•	participant satisfying one of the following criteria will not be eligible to participate in CCTG Study:
371	1.	Currently participating in another intervention study.
372 373	2.	Any imminent change in residence outside the driving distance of the ICCTG network within the next 24 weeks.
374	3.	Participant unlikely to be compliant due to medical or psychological problem.
375	4.	A history of having been previously treated with Cytoxan ® /cyclophosphamide.
376	5.	A history of pelvic radiation treatment.
377 378	6.	Having been previously treated with at least 100 mg TID of Elmiron ® or greater than 10 mg of hydroxyzine per day for greater than 12 consecutive weeks.
379	7.	Having had augmentation cystoplasty.
380	8.	Having had a cystectomy or cystolysis.
381 382	9.	Having had a neurectomy (i.e. hypogastric nerve plexus ablation) or implanted peripheral nerve stimulator which has affected bladder function.
383	10.	A history of a bladder calculus.
384	11.	A history of tuberculous cystitis.
385	12.	A history of neurologic disease or diabetic cystopathy.
386	13.	A history of malignant bladder tumors.
387	14.	A history of urethral cancer.
388 389	15.	Reports a urinary void with a maximum volume > 350 cc, as measured by a 24 hour-voiding diary.
390	16.	Currently has an active urethral calculus.
391	17.	Currently has a ureteral calculus.
392	18.	Symptomatic urethral diverticulum.
393 394	19.	Has an LFT $> 1.5$ times the respective institution's upper limits of normal at the Baseline 1 screening visit.
395	20.	Has abnormal blood coagualation tests results: PT or PTT (aPTT).
396	21.	Has platelet test results outside the respective institution's normal range.
397	22.	Reports any allergies to Elmiron ® or hydroxyzine.
398	23.	Currently taking cimetidine or currently on intravesical heparin.
399 400	24.	Chronic use (more than 3 out of 7 days each week) of greater than one gram of acetylsalicylic acid (e.g. aspirin, Bayer ® , Anacin ® , Excedrin ® , etc.).
401 402	25.	Chronic use (more than 3 out of 7 days each week) of aspirin replacement products (acetaminophen, NSAIDs, etc.) of more than the amount of milligrams in the

403 404		maximum single dose allowed by the Physicians' Desk Reference for prescription use, spread out over 24 hours.
405 406 407	26.	Chronic use (more than 3 out of 7 days each week) of sedating histamine-1 receptor antagonists (only those containing diphenhydramine, brompheniramine, or chlorpheniramine).
408	Exclusio	on criteria for men only:
409	27.	Having a residual urine volume >150 cc by ultrasound or catheter.
410 411 412	28.	Having had a TURP, TUIP, TUIBN, TUMT, TUNA, balloon dilation of the prostate, open prostatectomy or any other prostate surgery or treatment such as cryotherapy or thermal therapy.
413 414	29.	Currently being treated for chronic bacterial prostatitis as documented by a positive urine culture.
415	Exclusio	on criteria for women only:
416	30.	Having had uterine, cervical or vaginal cancer during the past 3 years.
417	31.	Having active vaginitis.
418	32.	Currently pregnant.
419	33.	Currently breastfeeding.
420	5.5	Deferral criteria
421 422 423 424 425 426	into has s for e and t	e are several physical conditions for which a participant will be deferred from entry the ICCTG Study. Once it is formally ascertained that the condition is not present or subsided according to the time frame identified, the participant will be reconsidered ntry into the ICCTG Study. The following list identifies the conditions for deferment the criteria that a participant must meet in order to be evaluated further for entry into tudy:
427 428	1.	If a participant has initiated any new medications for IC during the past 4 weeks, he/she will be deferred until he/she has been on the same dose for at least 4 weeks.
429 430 431 432 433	2.	If a participant has undergone any of the following during the past 6 weeks: urethral dilation, cystometrogram, urodynamics, bladder cystoscopy /hydrodistention under general or regional anesthesia, or bladder biopsy under general or regional anesthesia, he/she will be deferred until at least 6 weeks from the date of the procedure.
434 435 436	3.	If a participant has had a positive urine culture and/or clinical evidence of bacterial UTI during the past 6 weeks, he/she will be deferred until the participant has been without the condition for at least 6 weeks.
437 438	4.	If a participant has had gross hematuria during the past 12 weeks, he/she will be deferred until the participant has been without the condition for at least 12 weeks.
439 440	5.	If a participant has active genital herpes or has had active genital herpes during the past 12 weeks, he/she will be deferred until the participant has been without the

- If a participant has received treatment with Elmiron® or hydroxyzine, he/she will be 442 6. 443 deferred until the participant has been off drug for a minimum of 12 weeks prior to 444 study entry. 445 7. If a participant has had any intravesical treatment, other than BCG during the past 446 12 weeks, he/she will be deferred until at least 12 weeks after the last treatment 447 received. 448 8. If a participant has received intravesical BCG during the past 24 weeks, he/she will 449 be deferred until at least 24 weeks have passed since the last dose of BCG. 450 9. If a participant has had a cystocele, rectocele, or urinary incontinence surgery, 451 he/she will be deferred until at least 24 weeks from the date of the procedure. 452 Deferral criteria for women only: 453 If a participant has had any form of transvaginal surgery, hysterectomy, prolapse, 10. 454 vaginal delivery or C-section, she will be deferred until at least 24 weeks from the 455 date of the procedure.
- 456 6 Participant Recruitment, Consent and Confidentiality
- 457 6.1 Participant recruitment, consent, and confidentiality

Participant recruitment will be conducted through the urology clinic at each of the
participating clinical sites. Participants may be self-referred or referred through their
primary physician (either solicited or unsolicited by the urology clinic). Participants
referred to the clinics with symptoms suggestive of IC will be introduced to the ICCTG
Study by the Research Coordinator and by a one-page brochure (Appendix D) describing
the RCT for protocol #1. Potentially eligible participants will then be asked whether they
are interested in participating in the study.

- 465 6.2 Informed consent
- Each clinical site will prepare an informed consent form following the guidelines of their
  local Institutional Review Board. The form will, at a minimum, contain a description of
  the potential risks, benefits, and expense to the subject, and identify risk management
  procedures and the risk-benefit ratio and alternative treatment (see basic elements of the
  proposed informed consent in Appendix E).
- 471 If the patient expresses interest in participating, he/she will be asked to sign the informed
  472 consent form. This form will provide consent for both the screening procedures and the
  473 follow-up procedures. Prior to signing the informed consent, the Research Coordinator
  474 will review the details of the consent form orally with the participant, and answer any
  475 questions that the participant has concerning participation in the ICCTG Study. The
  476 original signed consent form will be kept in the participant study file at the clinical site,
  477 while a copy of the signed consent form will be given to the participant.
- 478
- 479

## 480 6.3 Participant confidentiality

481 Extensive efforts will be made to ensure that the participant's confidentiality is 482 maintained. Any forms or documents sent to the DCC will have all personal information 483 removed. Each participant will be assigned a unique study identification number. A log of 484 the participant names, participant ID numbers, and pertinent registration information (e.g. 485 home address, telephone number, and emergency contact person) will be maintained in a 486 locked file cabinet at each clinical site. The staff at the DCC will not have access to this 487 log. Only the participant ID number and initials will be given to the Data Coordinating 488 Center staff and entered into the ICCTG Study data base. Any communication between 489 the Data Coordinating Center staff and the clinical site staff regarding participant data will 490 occur via this participant ID number.

## 491 **7 Endpoints**

#### 492 7.1 Primary Endpoints

493 The primary endpoint will be a participant-reported global evaluation of improvement at 494 24 weeks or withdrawal, whichever comes first, relative to overall baseline symptoms. A seven point scale centered at zero will be used: -3) markedly worse; -2) moderately 495 496 worse; -1) slightly worse; 0) no change; +1) slightly improved; +2) moderately improved; 497 and +3) markedly improved. Participants who answer either +2) moderately or +3) 498 markedly improved on the primary endpoint will be considered to be responders. 499 Participants who withdraw from the study for any reason (e.g. adverse events or 500 participant choice) prior to the 24 week endpoint exam will be considered treatment 501 failures. Following standard "intent-to-treat" methods, these withdrawals will be included 502 in the denominator of the response rates for evaluation of the primary endpoint (see details 503 in section 15 of this protocol).

## 504 7.2 Secondary Endpoints

505 A number of secondary outcome measures related to both specific symptoms and overall 506 symptom scores will be used to supplement the analysis based on the primary endpoint. 507 Two symptom questionnaires will be evaluated over time for all participants entered in the 508 trial and compared to the overall assessment of response. The IC Symptom and Problem 509 Index was validated in IC participants studied from multiple clinical centers, using 510 gynecologic outpatients as controls (52). The University of Wisconsin Symptom Score 511 was recently validated by [name] and his group, using data from the BCG trial (53). 512 Both of these instruments will be utilized to assess responsiveness to change over time as 513 measured by the primary endpoint.

514In addition to overall symptom scores collected via these questionnaires, participants will515report their three primary symptom domains of pain/discomfort, urgency, and frequency516repeatedly over time. These measures are identical to those used in the ICDB Study517(6,54). Briefly, pain/discomfort and urgency are rated by the participants on a 10-point (0518-9) Likert scale, and frequency (and related volume measures) is assessed via a 24-hour519voiding log. A series of ongoing analyses of these ICDB data using latent variable

- 520 modeling of multiple measures of pain/discomfort suggest that this overall 10-point Likert
  521 scale for pain/discomfort has high internal consistency (55).
- Additional secondary analyses will be conducted to compare the impact of initiation or
  increased usage of narcotics during the follow-up period, and examination of the effects of
  other IC treatments that may represent "rescue medication" to compensate for lack of
  efficacy of the study agents. Details of both the primary and secondary analyses are
  described in section 15 of the protocol.

#### 527 8 Treatment Procedures

- 528 Participants meeting all inclusion criteria at Baseline Visit 2 will be randomized to one of the
- 529 four treatment arms as displayed previously in Figure 1 (Section 2). Each participant will
- 530 receive a four-week supply of blister packs containing green capsules (hydroxyzine or its
- 531 matching placebo) and one sealed bottle containing white capsules (Elmiron® or its matching
- 532 placebo). The study medications will be labeled according to regulatory requirement per Code of
- 533 Federal Regulations (CFR) 312.6 (56). This supply is designed to provide adequate medication
- 534 for the dose finding/stabilization phase for the green capsules and the fixed daily supply for the
- 535 white capsules for the three weeks prior to the first follow-up clinic visit. The Research
- 536 Coordinator will provide explicit instructions to the participant at the time of randomization and
- 537 dispensing of study drugs.
- The participant will be instructed to take three white capsules per day. If possible, he/she should
  try to take his/her white capsules eight hours apart, depending on his/her schedule. For example,
  the participant might take them at 6:00 a.m., 2:00 p.m. and 10:00 p.m. The participant should
- also take them on an empty stomach, either one hour before or two hours after a meal.
- Secondly, the participant will be instructed to take one or two green capsules per day, at bedtime.
  He/she may take the green capsule at the same time that he/she takes the third white capsule of
  the day. In order to find the maximal tolerable dosage for the green capsules, the blister cards
  will be prepared and labeled separately for weeks 1, 2 and 3. The blister card for week 4 will be
  identical to the card for week 3, and is provided to ensure a continuous supply prior to the 3week clinic visit, which may not fall exactly on the 21st day of follow-up.
- 548 Ø The blister card for week 1 will contain only 1 row of 7 green capsules, labeled as
  549 "Dose 1". The participant will be instructed to take only one green capsule per day, at bedtime.
- 551 Ø The blister card for week 2 will have two rows, labeled as "Dose 1" and "Dose 2". The participant will be instructed to begin week 2 by taking one green capsule per day, at bedtime, labeled "Dose 2". If for any reason, the participant can not tolerate "Dose 2", he/she will be instructed to call the Research Coordinator, and get approval to switch back to "Dose 1" for the remainder of week 2.
- 556 Ø The blister card for week 3 will have three rows, labeled "Dose 1", "Dose 2", and
  557 "Dose 3". For participants successfully completing week 2 on "Dose 2", they will be
  558 instructed to progress to "Dose 3" IN ADDITION to "Dose 2". That is, participants
  559 will be instructed during week 3 to take 2 green capsules per day at bedtime, the
  560 capsule in the "Dose 2" column AND the capsule in the "Dose 3" column. This will be
  561 clearly labeled on the week 3 blister pack. If for any reason, the participant cannot

tolerate "Dose 3", s/he will be instructed to call the Research Coordinator, and get
approval to switch back to "Dose 2" for 2 days then re-attempt "Dose 3" for the
remainder of Week 3. This process will be monitored closely by the Research
Coordinator so that the participant may comfortably be established on the dose that
they can tolerate for the maintenance phase of the study.

567 Ø Each participant will be provided with an extra blister card (Week 4) for use during
568 week 4, in the event that he/she cannot schedule his/her 3 week follow-up clinic visit
569 within exactly 21 days after the first visit. The participant should continue taking
570 his/her medication until the next office visit.

571 Participants will be instructed to take one or two green capsules each day, at bedtime. As a 572 result, there may be one unused capsule left over for each day of week 2, and one or two unused 573 capsules left over for each day of week 3. In an attempt to find the maximum tolerable dosage of 574 the green capsules, the participant may request, and the Research Coordinator may agree, to 575 change the participant's target dose for either weeks 2 or 3. However, the participant will be 576 instructed not to make this change in dose without consultation and approval from the Research Coordinator. The participant will be informed that dose stabilization is a crucial aspect of the first 577 578 3 weeks of follow-up. The RC will contact the participant at the end of weeks 1 and 2 to 579 determine treatment tolerability.

580 Prior to the clinic visit at the end of three weeks of follow-up, the Research Coordinator will 581 contact the participant to determine the maximum tolerable dose (either dose 1, 2 or 3) for the 582 green capsules. Depending on this response, the drug distribution center will ship one sealed 583 bottle of green capsules (at the selected dose) to the clinical center in overnight mail on time for 584 the 3 week follow-up visit. An additional sealed bottle will be dispensed to the participant at 585 clinic visits at weeks 10 and 17. The supply of green capsules in each sealed bottle is designed 586 to be adequate for taking one or two green capsules each day, at bedtime, for the following 7-8 587 weeks until the next clinic visit.

588 If during this drug maintenance phase, participants determine that the sedative adverse

experience is unpleasant, participants may request to de-escalate their drug dose one time only.
This decision can only be made in consultation with and approval from the study Principal
Investigator and Research Coordinator. The participant and Research Coordinator will then
determine if and when the participant can escalate the drug dose to the original level. These
changes will be documented by the participant in his/her Daily Medication Log, and by the
Research Coordinator in the participant study file.

The participant will be instructed that if at any time he/she should miss a daily dose, he/she should take the next dose at the usual time. The participant may not "double-up" a dose. The participant will be instructed to save the blister cards (during the first 3 weeks) and bottle, even if they are empty, and return all study medications at each follow-up visit, to assist the study in compliance monitoring.

600	8.1	Elmiron®
601		8.1.1 Dosing schedule and justification
602		The prescribed dose for $\text{Elmiron}^{\text{(BPS)}}$ will be one 100 mg capsule, three
603		times a day (TID). This dose corresponds to that used in the placebo-controlled
604		clinical trials which showed a significant difference between PPS and placebo

605 606 607 608 609 610 611 612 613		
 
(27-29). It is recommended from these studies that Elmiron® be taken at least two hours after a meal and at least one hour before the next meal. The white capsules will be provided in sealed bottles.
 
8.1.2 Drug manufacturing and packaging
 
Elmiron® will be manufactured centrally in one complete batch of active drug by the pharmaceutical manufacturer (ALZA™ Corporation located in Mountain View, CA). The entire quantity of active drug capsules will be shipped to the drug packaging and distribution center for packaging into sealed bottles, labeling and distribution directly to the clinical center, with the participant's
 

614 615	8.2	five-digit randomization number on the label. Placebo for Elmiron®
616		8.2.1 Dosing schedule
617 618 619		The placebo capsules are manufactured to appear identical to the Elmiron ® capsules and will be taken on the same schedule of one capsule three times a day (TID), two hours after and one hour before a meal.
620		8.2.2 Placebo manufacturing and packaging
621 622 623 624 625 626 627		A matching placebo (identical white capsules containing microcrystalline hydroxymethl cellulose, magnesuim stearate) for Elmiron ® will be manufactured centrally in one complete batch by the pharmaceutical manufacturer (ALZA ™ Corporation). The entire quantity of placebo capsules will be shipped to the drug packaging and distribution center for packaging into sealed bottles, labeling and distribution directly to the clinical center, with the participant's five-digit randomization number on the label.
628	8.3	Hydroxyzine
629		8.3.1 Dosing schedule and justification
630 631 632 633 634 635 635 636 637 638 639		The target dose of hydroxyzine will be two green 25 mg capsules per day, taken at bedtime. However, in order to minimize loss of participants due to inability to tolerate the potential adverse experiences (drowsiness), the dosage of hydroxyzine will be titrated up slowly from 10 mg per day (week 1), to 25 mg per day (week 2), to 50 mg [{2} 25 mg capsules] per day (week 3). By the end of week 3, each participant, in close consultation with the Research Coordinator, will select their maximal tolerable dose. This dose will be selected to be the maintenance dose for the remainder of the 21 weeks of the follow-up period.
640 641 642 643 644 645 646		Although all participants are expected to develop some initial adverse experiences from this medication, predominately sedation, it has been shown that participants tend to become tolerant to these effects if a slow titration is used (48). In addition, the entire dose of hydroxyzine will be given as one or two capsules before bedtime to minimize sedation effects during waking hours the following day.

647 648 649 650 651 652 653 654 655 656 657 658 659 660 661 662 663 664 665 666 667 668 669 670 671 672	
 
Participants will be instructed to increase their dose at the beginning of each new week during the dose stabilization phase (weeks 1-3) of the follow-up period, if they are not experiencing adverse experiences. The titration upward will be stopped if the participant reports that the adverse experiences are unacceptable. The dose of the study drug will then be reduced to the previously tolerated next lower dose for the remainder of that week. A second attempt to increase the dose by one step will be attempted. If this produces unacceptable adverse experiences, the dose will be lowered to the next lower level and maintained for the duration of the remaining weeks of follow-up. If the participant tolerates the higher dose, doses will be increased a step every week up to a maximum of 50 mg. The titration will be governed by the following rules:
 
Participants will be encouraged to take the highest dose of medication tolerated.
 
If a participant reports mild to moderate sedation at a particular dose, s/he will be kept on that dose for an extra week before restarting titration.
 
If the participant reports severe adverse experiences, they will be encouraged to reduce their dose by one level, but continue on the medication.
 
If there are adverse experiences and there is adequate time, participants will be encouraged to try a higher dose.
 
All doses should be stabilized by the end of 3 weeks.
 

673	8.3.2 Drug manufacturing and packaging
674 675	Hydroxyzine will be purchased from a certified supplier by the drug packaging and distribution center. An adequate supply of 10mg and 25 mg capsules will
676	be purchased, and over-encapsulated into green "look alike" capsules containing
677	either 10 mg (Dose 1), 25 mg (Dose 2), of hydroxyzine. These green capsules,
678	almost identical in size to the Elmiron capsules, will be packaged into blister
679	cards, labeled separately for weeks 1, 2 and 3. The blister card for the first
680	week will contain only one 10 mg capsule for each day. The card for the second
681	week will contain a separate row of one 10 mg (Dose 1) and one 25 mg (Dose
682	2) capsule for each day. The card for the third week will contain all three doses,
683 684	10 mg (Dose 1), 25 mg (Dose 2), and 25 mg (Dose 3). An additional Week 4
684 685	card will be provided to each participant to ensure a continuous supply prior to the 3-week clinic visit, which may not fall exactly on the 21 st day of follow-up.
686	At the end of the titration period, during his/her follow-up clinic visit, each
687	participant will receive his/her maintenance dose in a sealed bottle .

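### Sections 8 and 8.3.1 give inconsistent titration rules for the green capsules: the Dose 3 retry interval differs, and the extra-week sedation hold does not fit the three-week schedule

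*Protocol*

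**What the plan says.** **Section 8.3.1.** The target is 50 mg at bedtime, reached through 10 mg in week 1, 25 mg in week 2 and 50 mg in week 3. Four of its rules bear on this point:

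- **Hold:** when someone describes "mild to moderate sedation at a particular dose, s/he will be kept on that dose for an extra week before restarting titration".
- **Step-back:** when adverse experiences are unacceptable, the dose is "reduced to the previously tolerated next lower dose for the remainder of that week", and a second attempt at the higher dose follows.
- **Deadline:** "All doses should be stabilized by the end of 3 weeks".
- **Fixing the dose:** by then each participant has chosen the highest dose they can tolerate. "This dose will be selected to be the maintenance dose for the remainder of the 21 weeks of the follow-up period".

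The same list encourages participants to take the highest dose they tolerate, and to try a higher dose despite adverse experiences when enough time remains.

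**Section 8.** It covers the same three weeks card by card and has no sedation hold. The move to Dose 3 in week 3 is "For participants successfully completing week 2 on" Dose 2. Someone who cannot tolerate Dose 3 goes back to Dose 2 "for 2 days then re-attempt" Dose 3 within week 3. The coordinator may agree to "change the participant's target dose for either weeks 2 or 3". The coordinator establishes the maintenance dose by contact before the week 3 visit, and a bottle at that dose is shipped for the visit. During maintenance, section 8 allows one step down and a possible return to the level held before it. It gives no route to a first step up.

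**The concern.** The two sections govern the same capsules in the same weeks, and a coordinator cannot follow both to the letter. Two participants with the same mild sedation on 25 mg in week 2 could be treated differently: one kept at 25 mg under section 8.3.1, the other moved to 50 mg under section 8.

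What is at stake is the dose received and what the trial learns about the target dose. Tolerability of hydroxyzine is a primary objective (section 2). The trigger for a hold is not exotic, since section 8.3.1 says that "all participants are expected to develop some initial adverse experiences from this medication, predominately sedation". Section 12.1 says the drowsiness usually passes within days. A short-lived effect in week 1 or 2 could therefore set the dose for the following 21 weeks, and 25 mg could be recorded as the highest tolerated dose of someone who never took 50 mg.

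**Working it through.** **Inputs, all from sections 8 and 8.3.1.** Three dose levels (10, 25, 50 mg); one level per week; a hold adds one week at the current level; the dose is fixed at the end of week 3; maintenance lasts 21 weeks. Follow-up is 24 × 7 = 168 days, of which maintenance is 21 × 7 = 147 days.

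**The plan's own schedule.** Without a hold the path is 10/25/50. All three weeks are used and 50 mg is reached in week 3, as stated. Exposure is 7 × (10 + 25 + 50) + 147 × 50 = 595 + 7,350 = 7,945 mg.

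**With holds, applying section 8.3.1 literally:**

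| Hold at | Weeks 1/2/3 (mg) | 50 mg first due | Days at 25 mg | Total (mg) | Share of 7,945 |
|---|---|---|---|---|---|
| none | 10/25/50 | week 3 | 7 | 7,945 | 100% |
| 10 mg | 10/10/25 | week 4 | 7 + 147 = 154 | 7 × 45 + 147 × 25 = 3,990 | 50.2% |
| 25 mg | 10/25/25 | week 4 | 14 + 147 = 161 | 7 × 60 + 147 × 25 = 4,095 | 51.5% |
| 10 and 25 mg | 10/10/25 | week 5 | 154 | 3,990 | 50.2% |

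A hold first triggered at 50 mg does no harm, because 50 mg has already been taken. The percentages assume that the held participant would have tolerated 50 mg from week 3.

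**Dose 3 retry.** Week 3 is days 15 to 21. Suppose Dose 3 fails on day 15.

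- *Section 8:* Dose 2 on days 16 and 17, retry on day 18, four nights of the week left.
- *Section 8.3.1:* Dose 2 to day 21, so the second attempt starts on day 22 at the earliest. That is week 4, after the dose has been chosen.

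Even the 2-day rule has a limit. Counting the two nights from the day after failure, a failure later than day 18 cannot be retried inside week 3.

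**If 50 mg could be tried after week 3 and succeeded:**

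- From the start of week 4: 315 + 147 × 50 = 7,665 mg, or 420 + 7,350 = 7,770 mg (96 to 98% of 7,945).
- From the end of week 6 (21 days at 25 mg, 126 at 50 mg): 315 + 525 + 6,300 = 7,140 mg, or 420 + 525 + 6,300 = 7,245 mg (90 to 91%).
- From the end of week 10 (49 days at 25 mg, 98 at 50 mg): 315 + 1,225 + 4,900 = 6,440 mg, or 420 + 1,225 + 4,900 = 6,545 mg (81 to 82%).

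**The case against.** The strongest defence is that section 8.3.1 already ranks its instructions: hold for sedation, try higher if time allows, stop at three weeks. Slow titration is a stated choice to limit dropout, and withdrawals count as failures (section 7.1). On this reading the deadline is a deliberate cut-off. Section 8 may simply be silent on holds rather than opposed to them. Its week 3 card carries Doses 1 and 2 as well as Dose 3, so a hold can be supplied. Sites also work from a Manual of Procedures that is not shown.

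Much of this stands. A reader might infer that a held participant cannot reach 50 mg; the documents do not support that, because the coordinator may change the target dose in weeks 2 or 3 and the time-permitting clause encourages a higher dose. A reader might also infer from the expectation of sedation that most participants on hydroxyzine will be held. The same passage says tolerance tends to develop with slow titration, and section 12.1 calls the drowsiness short-lived, so many may be clear by the next step.

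What does not stand is that these clauses resolve the conflict. After a one-week hold the three-week schedule leaves no time for the time-permitting clause to use, unless the hold itself is cut short. The coordinator's power is permissive. The Dose 3 step-back is a plain difference between two explicit rules, not silence. The week 4 card, although it holds Dose 3, is provided to cover a late week 3 visit and is not described as a titration week.

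**Conclusion.** The inconsistency is real and should be corrected. It has two parts of different weight.

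1. The Dose 3 step-back is a direct contradiction: 2 days in section 8, the rest of the week in section 8.3.1. Under the latter, the promised second attempt falls after the dose has been chosen. In this case 50 mg has been tried once; what is lost is the retry.
2. The extra-week hold does not fit the three-week schedule and has no counterpart in section 8. Read literally, one hold at 10 or 25 mg leads to maintenance at 25 mg with 50 mg untried, for 154 or 161 of 168 days at 25 mg and 50 to 52% of full-schedule exposure. This assumes that neither coordinator discretion nor the time-permitting clause is used, and that 50 mg would have been tolerated.

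A reader might go on to infer a loss of power or a biased comparison for hydroxyzine. The protocol gives no hold rate and no dose-response, so no effect on power can be calculated. Placebo capsules follow the same schedule (section 8.4.1). Differences between sites are possible under the text but not shown.

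**What to change.** State one titration algorithm and use it in both sections, applied equally to the placebo capsules.

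- **Dose 3 intolerance:** step back to Dose 2 for 2 days and retry inside week 3. Delete the rest-of-week step-back for this level, and say what happens when intolerance arises too late in week 3 for a retry.
- **Sedation hold:** say how it fits with the week 3 deadline, so that 50 mg is tried when it can be tolerated. For example, say whether the hold may be shortened, or which rule gives way.

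This is a text edit to sections 8 and 8.3.1 and costs almost nothing.

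An option, not a requirement, is a single defined attempt at the next level after week 3 for participants held below 50 mg, with return to the previous dose if it fails. The week 6 call and the week 10 dispensing already exist to check and settle it. It would need its own capsule supply dispensed at the week 3 visit, because all study medication, including the week 4 card, is returned then. The price is a stable dose reached up to 7 weeks later (week 10 instead of week 3) in held participants, possibly with renewed sedation, in a protocol that treats dose stabilisation in the first three weeks as crucial. That trade-off is for the investigators to decide.
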